2.3.1.2 Important Potential Risks

The mechanism of action of tezepelumab suggests potential inhibitory effects on immune responses mediated by Th2 cells, leading to the possibility of diminution of the host's protective response to infection.

Severe infections

Severe infections are defined as infections that are SAEs, require treatment with systemic antiviral medications, intravenous antibiotics or medications for helminth parasitic infection, or require permanent discontinuation of study intervention.

To mitigate the potential risk of severe infections eligibility criteria will exclude vulnerable participants, and included participants will be monitored for infection with complete blood counts, including differential white cell count throughout the study; and through standard AE/SAE reporting. Participants using immunosuppressive medication within 3 months prior to screening; who have a history of a known immunosuppressive disorder; who have a history

of clinically significant infection prior to screening; and who have known active or suspected tuberculosis either treated or untreated, will be excluded.

Parasitic infestation/infections

Tezepelumab may decrease the protective response to helminth infection by blockade of TSLP.

To decrease the risk of parasitic infestation or infection, participants who have a history of clinically significant infection prior to screening and at screening, and participants with untreated systemic helminth parasitic infections or those at significant increased risk of systemic helminth parasitic infestations will all be excluded.

Serious hypersensitivity/allergic reactions (including immune complex disease)

As with any large molecule therapeutics, administration of tezepelumab may result in systematic and/or local reactions. Systemic reactions to large molecule therapeutics can be IgE or non-IgE-mediated and are generally characterized by signs and symptoms such as skin rash, urticaria, pruritus, local or diffuse erythema, angioedema, fever, chills, cough, dyspnea, wheezing, bronchospasm, nausea/vomiting, diaphoresis, chest pain, tachycardia or bradycardia, and/or hypotension, which can all be severe or life-threatening. Effects typically occur during or within several hours after study intervention, but may be delayed.

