8.3.6 Adverse Events of Special Interest

An AESI is an event of scientific and medical interest towards improving the understanding of the study intervention. An AESI may be serious or non-serious. For this study, AESIs include:

- Anaphylactic reactions
- Immune complex disease (Type 3 hypersensitivity reactions)
- Malignancy
- Helminth infections
- Severe infections which are defined as:
 - SAEs or
 - Requiring treatment with systemic antiviral medications, intravenous antibiotics or medications for helminth parasitic infection or
 - Requiring a permanent discontinuation of study intervention
- Injection site reactions
- Opportunistic infections
- Guillain-Barré Syndrome

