4.6.2.2 Presentation

All AE summaries will be presented by actual treatment group for the safety analysis set. A by- participant listing of all AEs will be provided; AEs occurring during screening will be included in the listing, but not summarized separately. The number and percentage of participants with on-treatment and on-study AEs will be tabulated separately by system organ class and preferred term. An event that occurred one or more times during a period will contribute one observation to the numerator of the proportion. The denominator of the proportion will comprise all participants in the safety population. On-treatment AEs will also be summarized by intensity/severity and separately, by causality/relatedness (as determined by the investigator). Should a participant report the same preferred term/system organ class within multiple intensity/severity or causality/relatedness categories, the participant's worst occurrence (most severe/most related) will be tabulated. Serious AEs, AEs leading to death, AEs leading to discontinuation from study intervention, and commonly occurring AEs (defined as those occurring in >5% of subjects in either treatment group) will be summarized by treatment group. AESIs will also be summarized descriptively by treatment group; serious infections will be summarized as part of the SAE by SOC and PT table in the SOC of infections and infestations and not in a separate table.

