Opportunistic infections will be defined using a pre-specified list of preferred terms (AZ defined SMQ).

Severe infections (as defined in the protocol)

Severe infections will use an investigator-driven definition, i.e. will be directly determined from what is entered on the eCRF.

A subject will be considered to have this AESI if the subject has at least one preferred term with AE onset date during the relevant study period for analysis, which satisfies the following:

- “AE Category” on Adverse Events eCRF page marked as “Severe Infection”, and one or more of the following:
 - AE is serious (“Serious” on Adverse Events eCRF page marked as “Yes”), or
 - AE required treatment with antiviral medications, intravenous antibiotics or medications for Helminth parasitic infection, or
 - AE resulted in permanent discontinuation of study drug (“Action taken, investigational product” on Adverse Events eCRF page marked as “Drug permanently discontinued”).

SIGNATURE PAGE

This is a representation of an electronic record that was signed electronically and this page is the manifestation of the electronic signature

Document Name: d5180c00031-sap-ed-2		
Document Title:	Statistical Analysis Plan Edition 2	
Document ID:	CCI [REDACTED]	
Version Label:	3.0 CURRENT LATEST APPROVED	
Server Date (dd-MMM-yyyy HH:mm 'UTC'Z)	Signed by	Meaning of Signature
28-Mar-2022 15:05 UTC	PPD [REDACTED]	Content Approval
28-Mar-2022 12:35 UTC	PPD [REDACTED]	Content Approval
28-Mar-2022 14:35 UTC	PPD [REDACTED]	Author Approval

Notes: (1) Document details as stored in CCI [REDACTED], an AstraZeneca document management system.

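### The SAP's severe-infection AESI adds an eCRF category tick and omits 'systemic' for antivirals, so it does not reproduce the protocol definition it cites

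*SAP*

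**What the plan says.** The protocol defines a severe infection twice, in the same terms. Section 2.3.1.2 begins: "Severe infections are defined as infections that are SAEs, require treatment with systemic antiviral medications, intravenous antibiotics or medications for helminth parasitic infection", and then adds infections that force study treatment to stop for good. Section 8.3.6 repeats this in its AESI list as three alternatives: the infection is an SAE; "Requiring treatment with systemic antiviral medications, intravenous antibiotics or medications for helminth parasitic infection or"; "Requiring a permanent discontinuation of study intervention". Any one is enough, and neither section makes an eCRF category part of the definition.

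SAP 7.3 opens its entry with "Severe infections (as defined in the protocol"). It then states: "Severe infections will use an investigator-driven definition, i.e. will be directly determined from what is entered on the eCRF". To count, an event needs its adverse-event category "marked as “Severe Infection”, and one or more of the following": it is serious; "AE required treatment with antiviral medications, intravenous antibiotics or medications for Helminth parasitic infection"; or the action-taken field shows that study drug was permanently stopped.

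SAP section 2, which lists changes from the protocol's planned analyses, declares one AESI change, the addition of hypersensitivity reactions. It does not mention severe infections.

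**The concern.** A definition met by any one of three facts has become a definition that needs a site classification and one of those facts. The SAP's check on the tick works in one direction only. A ticked event must still meet a criterion, so wrong ticks are screened out, but nothing in the SAP looks for unticked infections that meet one. Apart from the antiviral wording, errors in the tick can therefore only lower the count.

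The category label makes missed ticks plausible. Protocol Appendix E uses the word severe as an intensity grade, for an event that is incapacitating, and warns against confusing severity with seriousness. A moderate viral illness given a systemic antiviral is a severe infection under section 8.3.6, yet an investigator thinking of intensity could leave the category blank.

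The missing word acts the other way. A ticked infection whose only qualifying feature is a non-systemic antiviral counts under the SAP but not under the protocol.

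Severe infection is the first of the important potential risks described in Protocol 2.3.1.2, for a drug whose mechanism is said there to raise the possibility of a weaker defence against infection. The AESI count is where a reader would look for it.

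**Working it through.** There is no planned figure to reproduce, so the check compares the two rules as written. Describe an infection AE by five yes/no attributes:

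- T: category ticked as severe infection
- S: serious
- X: systemic antiviral, intravenous antibiotic or anthelmintic needed
- Y: non-systemic antiviral needed
- D: study treatment permanently stopped

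The rules are:

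- Protocol 2.3.1.2 and 8.3.6: S or X or D
- SAP 7.3: T and (S or X or Y or D)

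There are 2^5 = 32 patterns.

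- **Protocol rule met:** 7 of the 8 combinations of S, X and D, times 2 for T and 2 for Y, gives 28.
- **SAP rule met:** T = yes and 15 of the 16 combinations of S, X, Y and D gives 15.
- **Both met:** T = yes, 7 combinations of S, X and D, times 2 for Y, gives 14.
- **Protocol only:** 28 − 14 = 14, all of them unticked.
- **SAP only:** 15 − 14 = 1, which is ticked with a non-systemic antiviral and nothing else.
- **Neither:** 32 − 14 − 14 − 1 = 3.

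The rules agree on 17 patterns and disagree on 15. These are counts of logical possibilities, not of expected events; the documents give no frequencies.

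Next, see where the 14 unticked patterns would still be visible. SAP 4.6.2.2 says that "serious infections will be summarized as part of the SAE by SOC and PT table", and AEs leading to discontinuation of study treatment have their own summary. Patterns with S or D present number 3 × 2 × 2 = 12 (three combinations of S and D, two of X, two of Y), so these 12 appear in at least one of those summaries. The other 2 have S = no, D = no, X = yes, with Y either way.

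Those 2 shrink further. SAP 7.3 identifies helminth infections from a dedicated eCRF page and opportunistic infections from a pre-specified term list, and neither route uses the severe-infection tick. What remains is a non-serious, non-discontinuing infection, neither helminth nor opportunistic, treated with a systemic antiviral or intravenous antibiotic. It would be in the general AE tables by SOC and preferred term and in the AE listing, without being identified as a severe infection.

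On scale, about 100 participants randomized 1:1 gives about 50 per arm, so one participant missed is 1/50 = 2 percentage points in that arm.

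**The case against.** The strongest reply is that the tick is how the protocol definition is applied. The definition concerns infections, so some field has to mark an AE as one; otherwise any SAE would qualify. SAP 7.3 uses the same category field for injection site reactions. Protocol 8.3.6 gives investigators the criteria, so a site that follows it would tick when one is met, and the SAP criteria would then serve as confirmation. The amendment history in Protocol Appendix J also suggests that severe infections have eCRF data collection that other events do not. If ticking is complete, the SAP count falls short of the protocol count nowhere.

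That stands as a limit on the consequence: under-ticking is possible, not shown. It does not remove the mismatch. The documents supplied contain no eCRF completion instruction or reconciliation step that ensures complete ticking. The comparison with injection site reactions is also weak, because there the tick is the whole definition, whereas severe infection has criteria of its own, two of which are named eCRF fields in the SAP entry.

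A reader might infer that unticked severe infections vanish from safety reporting. The documents do not support that, since most remain visible in the summaries described above. A reader might also infer that severe infection is the drug's main risk. Protocol 2.3.1.2 lists several important potential risks and does not rank them.

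On the word systemic, the reply largely succeeds as to size: the omission affects only ticked, non-serious, non-discontinuing events whose sole qualifying treatment is a non-systemic antiviral, and the SAP heading points back to the protocol. It remains a wording error.

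**Conclusion.** The point holds as a mismatch of definitions with a limited consequence. The SAP says it uses the protocol definition, adds a required tick, drops a qualifier, and declares neither change. An unticked infection that meets a protocol criterion is left out of the AESI count, and the main practical gap is the non-serious, non-discontinuing infection treated with a systemic antiviral or intravenous antibiotic.

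The effect cannot be sized. It depends on how completely sites tick the category and how often such infections occur, and the documents give neither. The conclusion rests on reading the SAP rule literally and on the absence of any visible reconciliation step; eCRF instructions not supplied here could narrow the gap to nothing. AESIs are summarized descriptively, no hypotheses are tested, and the antibody endpoints are unaffected. The change is worth making before the primary lock, but it does not threaten the trial's main conclusions.

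**What to change.** Make three changes to SAP 7.3:

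1. Restore the word systemic before antiviral medications.
2. Count any AE in the Infections and infestations SOC that is marked serious, or whose action-taken field shows study drug permanently stopped, whether or not the category is ticked.
3. For the treatment criterion, list unticked infection AEs with a concomitant antiviral, antibiotic or anthelmintic, and query them with sites under blind before the primary database lock. Apply the same pre-written rule to infections arising in follow-up before the final lock, because by then the sponsor and CRO are unblinded and only sites and participants remain blind.

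If the tick is kept as a requirement, remove the claim to follow the protocol definition and declare the difference in SAP section 2.

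The second change needs only programming on fields the SAP already names. The third needs data queries. A reader might assume the treatment criterion can be derived from existing data, but the documents do not show this: Protocol 6.5 lists reason, dates and, for asthma drugs, dose and frequency, and Protocol 8.3.2 lists the AE variables. Neither documents route for every drug or a link from an AE to its treatment. The total cost is some programming and a limited set of queries.
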